6. SELECTION AND WITHDRAWAL OF SUBJECTS

6.1. Subject Inclusion Criteria

No subject should be assigned to treatment until all eligibility criteria have been satisfied. To qualify for the study a subject must:

1. Be a male or female and be ≥ 18 years of age
2. If a female of childbearing potential, have a negative urine pregnancy test and be using an effective contraception method (ie, abstinence, intrauterine device [IUD], hormonal [estrogen/progestin] contraceptives, or barrier control) for at least one menstrual cycle prior to study enrollment and for one menstrual cycle following end of study, or be surgically sterile
3. Have symptoms of unilateral idiopathic adhesive capsulitis for at least 3 months but not more than 12 months before the screening visit and be in Stage 2 (frozen or adhesive stage), as determined by the investigator
4. Have normal range of motion in the contralateral shoulder, as determined by the investigator
5. Have restricted active range of motion (AROM) in the affected shoulder defined as: a deficit of at least 60° in total AROM in the affected shoulder as compared with the total AROM in the contralateral shoulder and a deficit of at least 30° in AROM in at least one of the following planes as compared with the contralateral shoulder:
 - Forward flexion
 - Abduction
 - External rotation
 - Internal rotation
6. Voluntarily sign and date an informed consent agreement approved by the Institutional Review Board/Independent Ethics Committee (IRB/IEC). The subject must also sign an authorization form to allow disclosure of his protected health information (PHI). The PHI authorization form and informed consent form may be an integrated form or may be separate forms depending on the institution.

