10.1.2. Efficacy

For ROM, baseline is before injection on Day 1. Baseline for all other efficacy parameters is the screening visit.

The primary endpoint is the change (degrees) from baseline to the Day 95 follow-up in active forward flexion in the affected shoulder.

Secondary endpoints are:

1. Change from baseline to Day 95 in ASES function sub-scale
2. Change (degrees) from baseline to the Day 95 follow-up in abduction
3. Change from baseline to the Day 95 follow-up in pain with movement using a 11-point VAS
4. Change (degrees) from baseline to the Day 95 follow-up in internal rotation
5. Change from baseline to the Day 95 follow-up in external rotation
6. Change from baseline to the Day 95 follow-up in ASES pain sub-scale
7. Investigator satisfaction with treatment at the Day 95 follow-up
8. Subject satisfaction with treatment at the Day 95 follow-up

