10.2. Statistical Methodology

10.2.1. Efficacy

Simultaneous hypothesis tests for all primary and secondary efficacy endpoints will be accomplished with a family-wise 5% significance level by applying a closed hierarchical testing procedure. Under this approach, the first test in the hierarchy that fails to reject its individual hypothesis at the 5% level requires that all hypotheses following the first non-significant hypothesis cannot be tested.

1. For the investigator assessment of improvement with treatment and subject satisfaction with treatment, a Wilcoxon rank sum non-parametric test will be performed to compare active to placebo.
2. Mixed-model ANOVA with factors for treatment group and visit will be performed to compare active to placebo for forward flexion, abduction, internal rotation, and external rotation, ASES function subscale, and pain with movement.

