APPENDIX A ACTIVE RANGE OF MOTION (AROM)

AROM in both the affected and unaffected shoulder will be measured with goniometry while the subject is seated comfortably, without assistance of others. Forward flexion, abduction, internal rotation with the elbow up to 90° abduction, and external rotation will be measured as shown in the following depictions.

Active Forward Flexion (Range: 0-180°)

1. To evaluate flexion, have the subject sit comfortably in a chair. Ask the subject to place his/her arm at their side, with the palm facing the hip. Stabilize the scapula and clavicle by cupping the superior aspect of the shoulder. This stabilization will also help keep the subject in an upright position and prevent the subject from leaning backwards.
2. The axis or center of the goniometer is placed at the lateral aspect of the center of the humeral head, just inferior to the lateral aspect of the acromion process. The stationary arm of the goniometer is parallel to the midline of the trunk (**Picture 1**).
3. Ask the subject to keep his/her palm medial and to slowly lift the arm in an anterior and upward direction to the limit of motion in elevation. Keep the stationary arm of the goniometer in midline of the trunk and the moveable arm of the goniometer pointed towards the olecranon process (**Picture 2**). Ask the subject to stop with the onset of shoulder pain.
4. The measurement should be repeated a total of three times. If the measurements are within 10 degrees of each other, please record the highest of the three measurements. If any of the measurements are greater than 10 degrees of each other, the sequence should be repeated. The unaffected arm should be measured first, followed by the affected arm.

[figure not shown]
Picture 1

Picture 2

Active Shoulder Abduction (Range: 0-180°)

1. To evaluate abduction, have the subject sit comfortably in a chair. Next have the subject place his/her arm at the side, with the palm facing the hip. No stabilization will be necessary while testing abduction.
2. The axis or center of the goniometer will be placed at the midpoint of the posterior aspect of the glenohumeral joint. The stationary arm of the goniometer will be lined up parallel to the sternum and the midline of the trunk (**Picture 1**).

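### The mixed model named for the change-from-baseline endpoints does not list the baseline value as a covariate, which gives up precision that data already collected could supply

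*Protocol*

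**What the plan says.** Section 10.1.2 defines the primary endpoint: "The primary endpoint is the change (degrees) from baseline to the Day 95 follow-up in active forward flexion in the affected shoulder". The continuous secondary endpoints are also changes from baseline. The same section fixes when baseline is taken: "For ROM, baseline is before injection on Day 1". For the other efficacy measures it is the screening visit.

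Section 10.2.1 gives the analysis: a mixed-model ANOVA with "factors for treatment group and visit will be performed to compare active to placebo". The synopsis repeats it. Neither place names a baseline covariate, and the method is called ANOVA.

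Appendix A gives active forward flexion a range of 0 to 180 degrees. Section 6.1, inclusion criterion 5, sets two conditions on motion. The first is "a deficit of at least 60° in total AROM in the affected shoulder", relative to the other side. The second is "a deficit of at least 30° in AROM in at least one of the following planes as compared with the contralateral shoulder". Forward flexion is one of four planes that can meet the second condition.

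Section 10.3 sizes the trial on the SD of the change score (30 degrees for forward flexion) with no allowance for baseline adjustment.

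**The concern.** A subject who starts with fairly good flexion cannot gain much before reaching the limit of the scale, while a very stiff subject can. Because the entry deficit may lie mainly in other planes, baseline flexion may vary among eligible subjects, and change is then likely to be negatively related to it. An analysis of change without baseline leaves that explainable variation in the error term.

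What is at stake is the width of the confidence interval and the power of the primary test. The primary test opens the whole hierarchy: under section 10.2.1, once a test "fails to reject its individual hypothesis at the 5% level", nothing after it may be tested. The margin over 90% is also thin. With the formula shown in the working, power for 15 degrees is 90.1% if the SD of change is 31 and 88.2% if it is 32.

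**Working it through.** **Inputs.** From section 10.3: 240 evaluable subjects at 3:1 (180 and 60), difference 15 degrees, SD of change 30. From section 10.2.1: 5% level, sidedness not stated, two-sided assumed. Not in the document: the correlation rho between baseline and Day 95 flexion, and the baseline SD. The registry results appended to the protocol report only SDs of change, so they do not supply either.

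**The plan's own figure.**
- SE = 30 × sqrt(1/180 + 1/60) = 30 × 0.1491 = 4.47 degrees.
- Power = Φ(15/4.472 − 1.960) = Φ(1.394) = 91.8% (91.6% with the noncentral t).
- Effect detectable with 90% power = (1.960 + 1.2816) × 4.472 = 14.5 degrees.
- 240/(1 − 0.20) = 300.

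The statement of at least 90% power is reproduced.

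**Effect of adding baseline, equal variances.** If baseline and Day 95 flexion both have variance s², the variance of change is 2s²(1 − rho) and the residual variance after adjusting Day 95 (or change) for baseline is s²(1 − rho²). The ratio is (1 + rho)/2. Keeping the SD of change at 30:

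| rho | variance ratio | SE (degrees) | detectable at 90% (degrees) | power for 15 degrees | N with the precision of 240 unadjusted |
|---|---|---|---|---|---|
| none (plan) | 1.00 | 4.47 | 14.5 | 91.8% | 240 |
| 0.2 | 0.60 | 3.46 | 11.2 | 99.1% | 144 |
| 0.5 | 0.75 | 3.87 | 12.6 | 97.2% | 180 |
| 0.7 | 0.85 | 4.12 | 13.4 | 95.3% | 204 |
| 0.8 | 0.90 | 4.24 | 13.8 | 94.2% | 216 |

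Each SE is 4.472 × sqrt(ratio), and the last column is 240 × ratio. The higher the correlation, the smaller the gain over a change score.

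**Unequal variances.** Let k = SD(Day 95)/SD(baseline). The ratio becomes k²(1 − rho²)/(1 + k² − 2·rho·k). At rho = 0.5:
- k = 0.8: 0.48/0.84 = 0.57
- k = 1.0: 0.75
- k = 1.3: 1.2675/1.39 = 0.91
- k = 1.5: 1.6875/1.75 = 0.96

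In the last case SE = 4.39, the detectable effect is 14.2 degrees and power is 92.7%, about one percentage point above the plan. The ratio reaches 1 when rho × k = 1, where change is unrelated to baseline and adjustment gains nothing.

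**Chance imbalance.** At rho = 0.5 with equal variances, the unadjusted variance is 4.472² = 20.0 and the adjusted variance is 15.0. The difference of 5.0 is the part due to chance differences in baseline between arms. A one-SE imbalance therefore moves the unadjusted estimate by sqrt(5.0) = 2.2 degrees. That 5.0 is already inside the 20.0, so it is the same loss seen from another side.

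These figures treat the Day 95 comparison as a two-group comparison with complete data, as the sample size calculation does. A repeated-measures fit would differ somewhat.

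**The case against.** The best defence is that nothing in the plan is invalid. The sample size rests on the unadjusted SD of change, the planned analysis reaches its own target, and randomisation keeps an unadjusted comparison unbiased. All of this stands. A reader might infer that leaving baseline out biases the treatment effect or makes the power statement false. The document supports neither inference.

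A second defence is that section 10.2.1 is a one-sentence summary. It speaks of factors, does not say they are the only terms, and leaves the covariance structure and other details open; covariates are often settled in the SAP, which is not shown. This has some force. It is why the point is put as the terms named, not as proof that baseline would never be used. But the protocol does list terms, calls the method ANOVA, and says the same in the synopsis. An SAP that added baseline would have to extend the protocol's model.

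Third, the gain is easily oversold. Quoting only rho of 0.2 to 0.5 would suggest that 144 to 180 subjects would do the work of 240. That is the favourable end and needs equal variances. Entry restricts motion at baseline and response may vary, so a larger spread at Day 95 is plausible. Nor can wide variation in baseline flexion be taken as given, because entry also requires the 60-degree total deficit and Stage 2 disease.

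Finally, chance imbalance with about 60 evaluable placebo subjects might be read as a harm on top of the wider interval. It is not, because the unadjusted standard error already includes it.

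**Conclusion.** The point holds as a recommendation on efficiency. The named model leaves out a covariate that is already collected and probably prognostic for the response. The planned analysis remains unbiased, and its stated power of at least 90% is correct at 91.8%.

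That baseline is missing from the named terms is plain from the text. That adjustment would help rests on a negative correlation of change with baseline, which the scale limit and the entry criteria make likely but do not prove. How much it would help cannot be read from the document. Under equal variances and rho of 0.2 to 0.8, the detectable effect falls by between 0.7 degrees (14.5 to 13.8) and 3.3 degrees (14.5 to 11.2). With a larger spread at Day 95 the gain can be close to nil. The change is worth making because it is nearly free and protects the test that opens the hierarchy, not because the present plan fails.

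**What to change.** Amend section 10.2.1 and the synopsis so that the mixed model for each continuous primary and secondary endpoint includes that endpoint's own baseline value, as defined in section 10.1.2, as a covariate together with baseline-by-visit. Word it to cover the ASES pain sub-scale too, which the sentence's list of endpoints does not name. Carry the same terms into the SAP before unblinding.

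Keep 300 subjects: the size of the gain is unknown, so it should not be spent on a smaller trial.

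The cost is wording and a few degrees of freedom. With one baseline slope per post-baseline visit this is seven for range of motion (Days 8, 22, 29, 43, 50, 64 and 95) and four for the patient-reported scales (Days 22, 43, 64 and 95). No new measurement, visit or subject is needed.

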10.2.2. Safety

Adverse events will be summarized for the active and placebo groups with the proportion of subjects reporting each event.

Actual values and change from baseline in vital signs and laboratory test parameters will be summarized for the active and placebo groups with descriptive statistics at each visit obtained.

10.2.3. Immunogenicity

Anti-AUX-I and anti-AUX-II antibodies levels and neutralizing antibodies to AUX-I and AUX-II will be summarized using descriptive statistics.

10.3. Determination of Sample Size

A sample size of 240 subjects with a 3:1 allocation ratio is sufficient to detect the following deltas between active and placebo for the following primary and secondary parameters with power $\geq 90\%$, based on results observed in Study AUXCC-870:

Endpoint (Change from Baseline)	Delta=AA4500-Placebo
Forward Flexion(SD=30 degrees)	15 degrees
Abduction(SD=30 degrees)	15 degrees
External Rotation(SD=25 degrees)	15 degrees
Internal Rotation(SD=20 degrees)	10 degrees
Function (SD=15 points)	10 points
Pain(SD=15 points)	10 points

CONFIDENTIAL INFORMATION
Auxilium Pharmaceuticals, Inc.
AUX-CC-871-Protocol- 20SEP13

Assuming a dropout rate of 20%, then planned sample size is 300 subjects (225 AA4500 and 75 Placebo) is sufficient to insure each of the primary and secondary endpoints have sufficient power to detect meaningful differences.

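### The 90% power in Section 10.3 is stand-alone power; under the hierarchy of Section 10.2.1 the chance of claiming abduction and later secondaries is lower, about 75–88% for all six tabulated endpoints together

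*Protocol*

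**What the plan says.** Protocol Section 10.3 opens with the claim "A sample size of 240 subjects with a 3:1 allocation ratio is sufficient to detect the following deltas between active and placebo". The power attached is at least 90%, and the effects come from Study AUX-CC-870. Its table lists six changes from baseline: forward flexion, abduction, external rotation, internal rotation, function and pain. After inflation for 20% dropout, the section says that 300 subjects (225 and 75) "is sufficient to insure each of the primary and secondary endpoints have sufficient power to detect meaningful differences".

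Section 10.2.1 covers all primary and secondary endpoints at a "family-wise 5% significance level by applying a closed hierarchical testing procedure". Once one test in the sequence fails at 5%, "all hypotheses following the first non-significant hypothesis cannot be tested".

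Section 10.1.2 numbers the secondaries: ASES function, abduction, pain with movement, internal rotation, external rotation, ASES pain, the investigator's rating, the subject's rating. No section says that this numbering is the testing sequence. Section 10.3 mentions neither the hierarchy nor any correlation between endpoints.

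**The concern.** In a gated sequence a secondary endpoint can be claimed only if it and every endpoint ahead of it are significant. The relevant power is the probability of that joint event, which cannot exceed the smallest stand-alone power in the chain and is usually below it. Forward flexion starts at about 92%, so less than two percentage points remain before the chain falls under 90%. Two further endpoints in the table have the same standardized effect.

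What is at stake is how the secondary results are planned for and read. Someone relying on Section 10.3 would expect at least a 90% chance of a formal claim for abduction, the rotations and ASES pain if the assumed effects are true. The testing rule in the same protocol makes that chance smaller.

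**Working it through.** **Inputs.** From Section 10.3: 240 evaluable subjects at 3:1, so 180 on AA4500 and 60 on placebo, with the tabulated differences and SDs. From Section 10.2.1: each test at 5%, in sequence. Assumed because the protocol does not state them: two-sided tests, the order numbered in Section 10.1.2, and an equal correlation between the test statistics.

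I read the table's pain row as the ASES pain sub-scale. The registry record appended to the protocol scores it 0–50. On the 0–10 pain-with-movement scale a change lies between −10 and +10, so an SD of 15 is impossible there.

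**Step 1: reproduce the plan's figures.** For a standardized difference d = delta/SD, the standard error is √(1/180 + 1/60) = 0.1491, and power = Φ(d/0.1491 − 1.96).

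| Endpoint | d | d/0.1491 | Stand-alone power |
|---|---|---|---|
| Forward flexion | 15/30 = 0.50 | 3.354 | 91.8% |
| Abduction | 15/30 = 0.50 | 3.354 | 91.8% |
| Internal rotation | 10/20 = 0.50 | 3.354 | 91.8% |
| External rotation | 15/25 = 0.60 | 4.025 | 98.1% |
| Function | 10/15 = 0.667 | 4.472 | 99.4% |
| ASES pain | 10/15 = 0.667 | 4.472 | 99.4% |

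All six reach 90%, and 240/0.80 = 300. The stated figures are correct as stand-alone powers.

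**Step 2: apply the gate, six tabulated endpoints only.** Gated power for an endpoint is the probability that it and all earlier ones reject. With uncorrelated tests this is a running product:

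- forward flexion: 0.918
- function: 0.918 × 0.994 = 0.913
- abduction: 0.913 × 0.918 = 0.838
- internal rotation: 0.838 × 0.918 = 0.770
- external rotation: 0.770 × 0.981 = 0.755
- ASES pain: 0.755 × 0.994 = 0.750

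With equal positive correlation the joint normal probability was evaluated numerically:

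| Endpoint | 0 | 0.5 | 0.7 | 0.9 |
|---|---|---|---|---|
| Forward flexion | 92% | 92% | 92% | 92% |
| Function | 91% | 92% | 92% | 92% |
| Abduction | 84% | 86% | 87% | 89% |
| Internal rotation | 77% | 82% | 84% | 88% |
| All six | 75% | 81% | 84% | 88% |

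The last row is the probability that all six reject, so it does not depend on the order. It returns to 91.8% only at a correlation of 1.

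**Step 3: put pain with movement in its place.** It is secondary no. 3, ahead of both rotations and ASES pain, and has no stated difference or SD. Assuming d = 0.667, the figure for ASES pain is 75 / 81 / 84 / 88% at the same four correlations. Assuming d = 0.50, it is 69 / 78 / 81 / 86%.

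**Step 4: the upper bound on sample size.** If all 300 subjects contributed fully (225 and 75), the joint power of the six would be 89 / 91 / 92 / 94%.

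**The case against.** The strongest reply is that no number in Section 10.3 is wrong. Power per endpoint is a customary way to justify a sample size, the table reproduces, and the text never calls these figures probabilities of a claim under the hierarchy. That stands: this is a missing qualification, not an arithmetic error.

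A reader might also infer that the protocol promises at least 90% power for every secondary endpoint. It does not. The 90% belongs to the six tabulated rows, and the closing sentence speaks only of sufficient power. Pain with movement and the two ratings carry no power figure at all. For the same reason 75–88% is not the power of the last endpoint in the list. That endpoint is subject satisfaction, for which no effect is assumed.

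The size of the shortfall rests on assumptions. Zero correlation among four motions of one shoulder, together with function and pain in the same patient, is an extreme case, so 75% is a floor for the six tabulated endpoints rather than a best guess. The figures for abduction and internal rotation also depend on the assumed order. Finally, 240 is cautious: the mixed model can use partial data, and Section 6.3 asks for a final evaluation at withdrawal, so the effective number probably lies between 240 and 300.

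These points soften the size but do not remove the problem. The 90% statement is made for 240 subjects, and at that number abduction and every later tabulated endpoint stay below 90% even at a correlation of 0.9.

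**Conclusion.** The point holds as a mismatch between two sections of the protocol. With 240 evaluable subjects, the testing rule of Section 10.2.1 does not give 90% power to claim four of the five tabulated secondaries: abduction, internal rotation, external rotation and ASES pain. This rests on two-sided 5% tests, the Section 10.1.2 order and equal correlations up to 0.9. The joint figure for the six needs no assumption about order.

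It would be going too far to conclude that the trial is too small. The primary endpoint is taken as first in the sequence and keeps 91.8%, ASES function keeps 91–92%, the hierarchy still controls type I error, and the sample size is sound for the primary. The consequence is limited to overstated expectations for the later secondaries. The correction is worth making because it is free.

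**What to change.** Keep the sample size and amend Section 10.3 as follows:

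- Label the tabulated powers as per-endpoint powers that ignore the hierarchy.
- State the testing order and add a column with cumulative gated power for each endpoint over a stated correlation range, for example 0 to 0.9.
- Give an explicit difference and SD for pain with movement, and carry it through that column.
- Under the hierarchy, limit the statement of at least 90% to forward flexion and ASES function.
- Delete the assurance of sufficient power for each secondary endpoint, which now also covers three endpoints with no effect assumption. A single replacement range for all secondaries would not be right either: ASES function lies above 90%, ASES pain can fall to 69%, and for three endpoints nothing can be calculated from the protocol.

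The cost is protocol wording and less favourable stated powers for the secondaries. No extra subjects and no change to the tests are needed.

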11. ETHICS

11.1. Independent Ethics Committee or Institutional Review Board

Good Clinical Practice (GCP) requires that the clinical protocol, any protocol amendments, the Investigator's Brochure, the informed consent, and all other forms of subject information related to the study (eg, advertisements used to recruit subjects) and any other necessary documents be reviewed by an Independent Ethics Committee (IEC)/Institutional Review Board (IRB). IEC/IRB approval of the protocol, informed consent and subject information and/or advertising, as relevant, will be obtained prior to the authorization of drug shipment to a study site. Any amendments to the protocol will require IEC/IRB approval prior to implementation of any changes made to the study design.

